7.1 Baseline Considerations

7.1.1 Demographics

Demographics will be tabulated for the FAS as well as for subjects enrolled in LP0084-1369. Data will be presented by treatment location (face/chest or scalp) and treatment group within treatment location as well as overall by treatment group (ingenol disoxate versus vehicle). The protocol states that demographics will be presented by treatment group in the main trials and by country. However, from the analysis of the main trials it was found that treatment location is an important factor and therefore it was decided to present data by treatment group and location instead of by country. The demographic data, including age, from the time of randomization will be used. The analyses of demographics will be based on the planned treatment.

7.2 Analysis of Efficacy

The primary endpoint is time to first SCC in the treatment area. The event of an SCC is defined as AEs coded to the preferred term “Squamous cell carcinoma of skin” (MedDRA v. 18.1). The secondary time-to-event endpoint is time to first SCC or other skin neoplasia in the treatment area. The event of an SCC or other skin neoplasia is defined as AEs coded to preferred terms that are included in the standardised MedDRA query (SMQ) “Skin

Trial ID: LP0084-1369	Date: 27-May-2018	Version: 1.0 Page 8 of 14
-----------------------	-------------------	------------------------------

malignancies” (MedDRA v. 18.1). The analyses of efficacy endpoints will be based on the planned treatment.

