8.4.1 Adverse EventS of Special Interest and other Skin Neoplasia

All biopsies of KA, SCC or other skin neoplasia in the treatment area should be sent for central review in the IAC, Section [12.1](#). If there are any discrepancies between the local histology report and the central pathology review, there should not be any changes in the CRF. For the central review, the local pathology laboratory will send the relevant histology slides to the investigator who will forward the slides to the CRO for distribution to the adjudication committee. Only if the original slides cannot be sent is it acceptable to use new slides made from the same tissue block.

A biopsy should be considered in the following clinical situation:

- A new lesion in the treatment area that has bled on more than 2 occasions.
- Any papular lesion that measures more than 0.5 cm in diameter (0.2 inches).
- A presumed actinic keratosis that has been treated twice with cryosurgery without resolution.

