9.5 Follow-up for Final Outcome of Adverse Events

During the trial, the investigator should follow up for final outcome on all AEs (including SAEs). Once a subject leaves the clinical trial, the investigator should follow up on the outcome of all non-serious AEs classified as of possible/probable relationship to the investigational product for 2 months or until the final outcome is determined, whichever comes first. SAEs must be followed up until a final outcome has been established, i.e. the follow-up may continue beyond the end of the clinical trial.

10 Trial Product

Not applicable

11 Statistical Methods

Data on skin neoplasia from the 14 months observation time in the confirmatory phase 3 trials LP0084-1193, -1194, -1195, and -1196 will be combined with the data from the present trial.

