11.3.3 Exposure and Treatment Compliance

11.3.4 Analysis of Primary Endpoint

The null hypothesis is that there is no difference in time to first SCC between ingenol disoxate gel and vehicle gel. The hypothesis will be tested against the two-sided alternative that there is a difference between the two treatment groups.

Primary endpoint is time to first SCC in the treatment area from Visit 2 in trials LP0084-1193, -1194, -1195 and -1196.

Only the SCC confirmed by the IAC will be used in the primary endpoint analysis.

The annual and the 3-year and 2 months cumulative incidence of first event of SCC will be calculated for each treatment group (active and vehicle) in main trial using methods of survival analysis in the presence of censoring. The cumulative incidence rates will be presented by treatment group for the event of first SCC as primary endpoint. A proportional hazards model will be fitted if the model assumptions are valid. Log-rank test comparing the two treatment groups will be performed. For descriptive purposes, as an additional analysis, the difference in cumulative incidence rates between the two arms will be estimated and presented together with its 95% confidence interval. A landmark analysis will additionally be performed in order to exclude SCC and other neoplasia reported within the first 8 weeks which are not assumed to be associated with the trial treatment. This corresponds to left-truncation of the trial period at 8 weeks, the analysis will otherwise be conducted as above. Patients who experience a SCC before the 8-week landmark time point are excluded from the landmark analysis.

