11.3.5 Analysis of Secondary Endpoint

For the secondary endpoint, the null hypothesis is that there is no difference in time to first SCC or other skin neoplasia between ingenol disoxate gel and vehicle gel. The hypothesis will be tested against the two-sided alternative that there is a difference between the two treatment groups.

Secondary endpoint is time to first SCC or other skin neoplasia in the treatment area from Visit 2 in trials LP0084-1193, -1194, -1195 and -1196.

Trial ID: LP0084-1369	Date: 25-Jul-2017	Version: 2.0 Page 26 of 52
-----------------------	-------------------	-------------------------------

Only the SCC or other skin neoplasia confirmed by the IAC will be used in the secondary endpoint analysis.

Analysis of the secondary endpoint will be performed as outlined above for the primary endpoint.

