The most common AEs ($\geq 2\%$ of subjects in the active treatment group in the main trial) will be presented by treatment group.

Serious adverse events and withdrawal

SAEs will be evaluated separately and a narrative for each will be given. AEs leading to withdrawal from trial will be listed.

Adverse events of special interest

AESI will be presented by treatment group in the main trial. For the AESI the number of events with agreement and disagreement between data from the AE form in the CRF and data from the central review will be presented by treatment group. A narrative for each AESI will be given.

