12.1 Independent Adjudication Committee

In LEO ingenol trials, squamous cell carcinoma (SCC) and keratoacanthoma (KA) inside the treatment area have been defined as an AESI. KA may be difficult for some pathologists to distinguish from SCC and may be underreported due to the fear of misdiagnosing the malignant SCC. As many AK patients are prone to SCC as well as KA due to the heavy sun damage, it is of great importance that possible tumours that occur after treatment with ingenol disoxate are diagnosed correctly. An independent adjudication committee (IAC) has therefore been assembled to provide consistent evaluation of the incidence of KA in the patient population as opposed to the incidence of SCC. The IAC comprises 3 medical doctors, who are experts in dermatopathology.

All biopsies of AESIs and other skin neoplasia in the treatment area at any time during the trial will be sent to the IAC for central review, as described in sections [8.4](#) and [9.3.3](#).

See [Appendix 4: Contact list of LEO, protocol authors, vendors, trial committees and coordinating investigators](#) for contact details on all trial committee members.

13 Case Report Forms and Data Handling

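### SAP 7.2 defines SCC and neoplasia events by MedDRA coding alone, while the protocol counts only events confirmed by the adjudication committee, and neither document says which rule prevails

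*SAP*

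**What the plan says.** Protocol 11.3.4 is explicit for the primary endpoint: "Only the SCC confirmed by the IAC will be used in the primary endpoint analysis". Protocol 11.3.5 repeats the rule for the secondary endpoint: "Only the SCC or other skin neoplasia confirmed by the IAC will be used in the secondary endpoint analysis".

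The rule is not limited to the extension. Protocol 11.3.4 starts the clock in the main trials ("Primary endpoint is time to first SCC in the treatment area from Visit 2 in trials" LP0084-1193 to -1196). The opening of Protocol section 11 says that "Data on skin neoplasia from the 14 months observation time in the confirmatory phase 3 trials" will be combined with the extension data.

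SAP 7.2 defines the same events through coding. For the primary endpoint, "The event of an SCC is defined as AEs coded to the preferred term" for squamous cell carcinoma of skin, in MedDRA 18.1. For the secondary endpoint, the AE must be coded to a term in the skin malignancies SMQ. Neither definition mentions the IAC. SAP 7.2.1 and 7.2.2 then say that the endpoints are analysed as the protocol describes.

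On discrepancies between local histology and central review, Protocol 8.4.1 says "there should not be any changes in the CRF". For adverse events of special interest, Protocol 11.3.6.1 plans to tabulate "agreement and disagreement between data from the AE form in the CRF and data from the central review" by treatment group.

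**The concern.** The event definition drives everything downstream: the log-rank and likelihood ratio tests, the hazard ratio, the numerators of the incidence rates, the censoring of subjects without an event, and the exclusion of subjects with an event before Visit 7 from the landmark analysis. A programmer who follows SAP 7.2 literally counts coded SCCs that the IAC did not confirm. One who follows the pointer to the protocol does not. The result would then depend on a choice that nobody has written down.

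Two features of the trial give this weight. Protocol 12.1 explains that keratoacanthoma (KA) can be hard to tell from SCC and that the IAC was set up to evaluate the two consistently. Protocol 6.5 says that blinding is not maintained in the extension except for the IAC members. Read literally, SAP 7.2 therefore rests extension events on site diagnoses made without maintained blinding.

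**Working it through.** The check is mainly a comparison of texts.

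**1. Is the IAC rule current?** Yes. It stands in Protocol version 2.0. The SAP introduction describes the amendment to 11.3.4 and 11.3.5 as adding null-hypothesis text only.

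**2. Can the two rules select different lesions?** In the extension the CRF keeps the local diagnosis after a discrepant review (Protocol 8.4.1), so the coded AE does not carry the IAC result. Three rules can be read from the documents: coding alone (SAP 7.2 taken literally), coding plus IAC confirmation (SAP 7.2 read together with its pointer to the protocol), and IAC diagnosis alone (one reading of Protocol 11.3.4). For the primary endpoint they give:

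| Local coded term | IAC reading | Coding alone | Coding plus IAC | IAC diagnosis |
|---|---|---|---|---|
| SCC | SCC | counted | counted | counted |
| SCC | not SCC | counted | not counted | not counted |
| other, e.g. KA | SCC | not counted | not counted | counted |
| SCC | no result | counted | not counted | not counted unless a rule is set |

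The rules agree only in the first row. The third row matters for the remedy: adding an IAC filter to the coded events would still miss lesions coded otherwise that the IAC reads as SCC.

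**3. Is a change declared?** Protocol 11.3.8 requires changes from the planned analysis to be described and justified. The SAP does so for demographics by country (7.1.1) and for testing of AEs (7.3.1). The SAP text available for this check does not mention the IAC, and no Appendix I title refers to central review. The front matter and the start of the introduction were not available.

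**4. Can the effect be sized?** The only planning figures for the SCC rate are the upper confidence limits in Protocol 11.1. They reproduce with the Wald limit p + 1.96 × √(p(1 − p)/n):

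- p = 0.04, n = 800: 0.04 + 1.96 × 0.00693 = 5.36%
- p = 0.04, n = 400: 0.04 + 1.96 × 0.00980 = 5.92%
- p = 0.06, n = 800: 0.06 + 1.96 × 0.00840 = 7.65%
- p = 0.06, n = 400: 0.06 + 1.96 × 0.01187 = 8.33%

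All four match. They do not help here: Protocol 11.1 does not say whether its assumed rates are for coded or confirmed SCC, and the documents give no confirmation share, no reclassification share and no event count by arm. Rows 2 and 3 of the table move the count in opposite directions, so even the sign of the net change is open.

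**5. Do the rules apply in the main-trial period?** The protocol rule does, because the endpoint starts at Visit 2 of the main trials. Whether IAC results exist for that period is not shown. Protocol 12.1 says that biopsies "in the treatment area at any time during the trial will be sent to the IAC for central review", which describes this trial, and the main-trial protocols are not part of the documents.

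**The case against.** The strongest reply is that the two texts are compatible. SAP 7.2 can be read as the coding step and Protocol 11.3.4 as the confirmation step, with SAP 7.2.1 and 7.2.2 importing the latter. The SAP declares its departures elsewhere and declares none here, which favours reading the IAC condition as retained. Protocol 11.3.8 also allows a change to be explained in the trial report, so silence in the SAP is not by itself a breach.

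Much of this stands. A harmonised reading is available, and a reader who infers that IAC confirmation was dropped goes further than the documents do. But the pointer is general, it follows an explicit definition that differs, and nothing says which prevails. Silence fits an omission as well as it fits an undeclared change. The harmonised reading also leaves the third row of the table unresolved.

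Three other stronger readings are not supported:

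- **That main-trial lesions were not adjudicated.** The documents do not show this either way. Protocol 11.3.4 applies the IAC rule from Visit 2 of the main trials, which presupposes that such data exist.
- **That the trial loses a stated amount of power or precision.** Any such figure would need an assumed confirmation share and hazard ratio, for which the documents give no basis. The share of follow-up that falls in the main trials does not measure the effect either.
- **That results shaped the definition.** The SAP postdates the decision to stop, and SAP 6.4 reports that one subject had no event. Some event information was therefore known, which is a reason to make the rule explicit. It is not evidence of influence.

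**Conclusion.** The conflict is real and current. The protocol restricts both endpoints to IAC-confirmed events. SAP 7.2 defines the same events by coding, without that condition and without a declared change. Because the coded term in the extension is not updated after central review, the two rules can yield different primary and secondary event counts.

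This should be corrected before the analysis: it concerns the definition of the primary event, and SAP 7.2 taken literally contradicts the protocol. The direction and size of the effect on the treatment comparison are unknown. The conclusion rests on the text of the two documents and on no numerical assumption. It is limited by the SAP front matter that was not available, and by the absence of any information on adjudication in the main trials.

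**What to change.** In SAP 7.2:

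1. Define the primary event by the IAC diagnosis of SCC, and the secondary event by the IAC diagnosis of SCC or other skin neoplasia, whatever the local coded term. Coded SCCs that the IAC did not confirm are then excluded, and lesions coded otherwise but read as SCC by the IAC are included.
2. Keep the coded-AE definition as a labelled sensitivity analysis.
3. Name the source of the IAC data separately for the main-trial and extension periods.
4. Report by arm the number of events without an IAC result. Fix their handling only after checking whether main-trial lesions were adjudicated, and do not exclude them by default.

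If the coded-AE rule was intended as primary, declare and justify it as a change under Protocol 11.3.8 and show the IAC-based analysis beside it.

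The cost is a few sentences and a merge of IAC results with the AE data. Event counts may rise or fall. If main-trial lesions turn out not to have been adjudicated, many events may lack an IAC result, which is why that check must come before any rule for them.

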5.2 Secondary Endpoints

Time to first SCC or other skin neoplasia in the treatment area

Safety Evaluations: Adverse event frequency by MedDRA Preferred Term

6 Trial Design

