8.4 Adverse Events

Only AEs in the treatment area (including keratoacanthoma [KA], SCC, or other skin neoplasia) will be collected. AEs must be assessed and recorded as specified in section [9](#).

If Visit 1 does not coincide with Visit 11 of the main trial (LP0084-1193, -1194, -1195 and -1196) events in the treatment area for the period between the two visits must be recorded at Visit 2.

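### SAP 7.2 defines both time-to-event endpoints by coded adverse event terms, although the protocol admits only committee-confirmed events, and it leaves open whether keratoacanthoma counts

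*SAP*

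**What the plan says.** Protocol 5.2 names the secondary endpoint as "Time to first SCC or other skin neoplasia in the treatment area". Protocol 11.3.5 restricts what counts: "Only the SCC or other skin neoplasia confirmed by the IAC will be used in the secondary endpoint analysis". Protocol 11.3.4 has the same rule for the primary endpoint: "Only the SCC confirmed by the IAC will be used in the primary endpoint analysis".

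SAP 7.2 defines the events differently. For the primary endpoint: "The event of an SCC is defined as AEs coded to the preferred term" for SCC of skin. For the secondary endpoint, the event is any adverse event coded to "preferred terms that are included in the standardised MedDRA query" (SMQ) named Skin malignancies. Both use MedDRA version 18.1. Neither definition refers to adjudication or central review. SAP 7.2.1 and 7.2.2 then say that the endpoints will be analysed in line with the protocol.

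On scope, Protocol 8.4 groups KA with SCC and other skin neoplasia: "Only AEs in the treatment area (including keratoacanthoma [KA], SCC, or other skin neoplasia) will be collected". Protocol 9.3.3 makes KA an adverse event of special interest, and Protocol 12.1 says that the IAC was set up "to provide consistent evaluation of the incidence of KA in the patient population as opposed to the incidence of SCC".

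**The concern.** The endpoint labels are the same in both documents, but the events underneath are not. A programmer working from SAP 7.2 and one working from Protocol 11.3.4 and 11.3.5 would build different event datasets and report them under the same title.

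Two things are at stake. The first is the source of the diagnosis. The protocol expects KA and SCC to be confused locally and created a central committee to resolve that. Counting coded adverse events bypasses the committee for the primary endpoint as well as the secondary. The second is scope. A query titled for malignancies is not self-evidently the same set as SCC or other skin neoplasia. KA is a lesion that Protocol 9.3.3 links to local irritation or inflammation, so whether it counts bears directly on a comparison of a topical product with vehicle.

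**Working it through.** **Step 1. The plan's own figures.** The only related numbers are the precision limits in Protocol 11.1, which SAP section 5 ties to SCC. They reproduce as p + 1.96 × √(p(1 − p)/n):

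- p = 4.0%, n = 800: 4.0 + 1.36 = 5.36%
- p = 4.0%, n = 400: 4.0 + 1.92 = 5.92%
- p = 6.0%, n = 800: 6.0 + 1.65 = 7.65%
- p = 6.0%, n = 400: 6.0 + 2.33 = 8.33%

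All four agree with the protocol. They depend only on an assumed rate and an arm size, so they neither support nor weaken this point.

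**Step 2. The definitions side by side.**

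| | Protocol 11.3.4, 11.3.5 | SAP 7.2 |
|---|---|---|
| Primary event | SCC confirmed by the IAC | Adverse event coded to one SCC preferred term |
| Secondary event | SCC or other skin neoplasia confirmed by the IAC | Adverse event coded to a term in the Skin malignancies SMQ |
| Source of diagnosis | Central review | Adverse event form |

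**Step 3. Can the two sources differ for the same lesion?** Yes. Protocol 8.4.1 says that the CRF is not altered when local histology and central review disagree, so the coded term keeps the local diagnosis. Disagreement is expected: Protocol 12.1 describes KA as hard for some pathologists to tell from SCC, and Protocol 11.3.6.1 plans counts of agreement and disagreement by arm for events of special interest. The table list in SAP Appendix I contains no such table.

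**Step 4. Blinding.** Protocol 6.5 says that the main trials were blinded, but that in the extension only the IAC members stay blinded. For lesions arising in the extension, IAC confirmation is therefore the one blinded step left in ascertainment.

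**Step 5. Scope.** Protocol 8.4 and 8.4.1 list KA with SCC and other skin neoplasia. The SAP names the SMQ but lists none of its terms and does not mention KA. The content of the query is not in either document.

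**Step 6. Possible size, by assumption only.** Let N be the number of subjects with an event under the protocol and M the number under SAP 7.2. Let f be the share of N with no qualifying coded event, and u the share of M that the IAC would not confirm. The subjects common to both are N(1 − f) = M(1 − u), so M/N = (1 − f)/(1 − u). The documents give neither f nor u. Letting each run from 0 to 30%:

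- f = 30%, u = 0: 0.70/1.00 = 0.70
- f = 30%, u = 10%: 0.70/0.90 = 0.78
- f = u: 1.00
- f = 10%, u = 30%: 0.90/0.70 = 1.29
- f = 0, u = 30%: 1.00/0.70 = 1.43

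The count may fall, rise or stay the same. Even at a ratio of 1.00 the subjects counted can differ unless f and u are both zero.

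**The case against.** The strongest reply is that nothing has been replaced. SAP 7.2.1 and 7.2.2 refer back to the protocol, which carries the IAC rule, so the coded terms could be a first step that finds candidate lesions before confirmation. That reading is possible, but the SAP does not state it. It would also yield a third event set, because a lesion recorded locally as KA and read centrally as SCC would never become a candidate for the primary endpoint. The cross-reference shows that the SAP is inconsistent; it does not resolve the inconsistency.

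A reader might infer that the secondary endpoint has become narrower, or that KA has been dropped. The documents do not support either. A query's title does not show which terms it contains, and omitting confirmation can also add lesions that the IAC would reject. For the same reason, a local mix-up of KA and SCC moves a subject in or out of the secondary endpoint only if KA is excluded, which is unknown. For the primary endpoint it matters whatever the query contains.

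A reader might also try to turn an assumed share of KA and benign lesions into lost events or a shifted hazard ratio. No lesion counts or split by arm are given. In a time-to-first-event analysis, a subject with one excluded lesion still counts if another lesion qualifies.

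Three further points have some force. KA would still appear in the adverse event tables by preferred term, so any gap concerns the time-to-event analyses and not all reporting. Protocol 11.3.8 allows a change to be justified in the clinical trial report, so a justification may yet come, although it would then be written with the data in hand. And the documents do not show that every main-trial lesion went to the IAC, which may be a practical reason for using coded terms. If so, the SAP should say so.

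**Conclusion.** The point stands as a conflict over event definition that affects both time-to-event endpoints, and the primary endpoint is the more important of the two. The protocol requires IAC confirmation; SAP 7.2 uses coded adverse event terms and elsewhere defers to the protocol. Followed literally, SAP 7.2 gives events based on local diagnosis and, in the extension, without the only blinded step. The SAP explains other departures, such as presenting demographics by location and dropping tests on adverse events, but not this one.

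For the secondary endpoint there is a separate omission: the SAP does not say whether KA and non-malignant neoplasms count. That they are excluded is not established.

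The direction and size of the effect are unknown. The range of 0.70 to 1.43 rests entirely on the assumed 0 to 30% for each mismatch and shows only that the effect could go either way.

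**What to change.** In SAP 7.2:

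1. Define both endpoints by the first IAC-confirmed qualifying diagnosis in the treatment area.
2. List the qualifying diagnoses for the secondary endpoint, and state whether KA and non-malignant neoplasms count.
3. Keep the preferred-term and SMQ versions as supportive analyses, labelled as such, with their terms listed in an appendix.
4. Add the table comparing the adverse event form with central review, by arm, planned in Protocol 11.3.6.1.
5. Identify lesions without IAC review and state how they are handled.

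If the sponsor prefers coded terms as the main definition, the SAP should record this as a departure from Protocol 11.3.4 and 11.3.5 and justify it, as Protocol 11.3.8 requires.

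The cost is mainly wording, the supportive analyses and one table, since the protocol already sends treatment-area biopsies to the IAC. Item 5 could take more work. Only 562 of the 1243 randomised subjects entered the extension (562/1243 = 45%), so the other 681 contribute main-trial data only, and the documents do not show how far main-trial lesions other than SCC and KA were adjudicated.
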